3.1 Primary outcome

Cumulated pain (VAS 0-100 mm) upon ambulation in a 5-meter walk test on days 2-7 postoperatively after TKA surgery.

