7.1 Power calculation

Data from our previous study showed that pain during a 5-meter walk test at 24 h was the best predictor of cumulated pain on days 2-7 after TKA surgery [[name] et al. – IN PREPARATION]. With the optimal cut-off of VAS ≥ 45 , the mean (SD) cumulated pain during a 5-meter walk test on days 2-7 was 390 (208). A 50 % reduction in cumulated mean VAS upon mobilization days 2-7 postoperatively is clinically relevant. In a two-sided superiority design with a level of significance of 0.05 and a power of 80% we need two groups of 18 patients each. Assuming a small number of dropouts, 22 patients will be included in each of the two groups resulting in inclusion of 44 patients in total.

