7.2 Data analysis

All participants who meet the inclusion criteria and undergo randomization will be included in the intention-to-treat (ITT) population. The per-protocol (PP) population is defined as the group of patients who are randomized, receive the treatment to which they were randomly assigned, and complete their assessments without any major protocol deviations. The primary and secondary outcome analyses will each be performed for the ITT and PP populations. The primary endpoint along with other continuous data will be tested using independent samples t-test or Mann-Whitney U test as appropriate. The secondary outcomes will also be analyzed relative to the pain relief during the initial LA injection in the cryo group versus the remaining patients from both groups. A P -value < 0.05 is considered significant. Dichotomized data will be tested using Chi-square or Pearson's exact test. Uni- and/or multivariate analysis, where appropriate, will be made to test for independent variables. Missing values will be accounted for in the final statistical plan. Statistical calculations will be made using either R statistical software (Open source) or SPSS statistics (IBM, New York, USA).

The study will be registered at Clinicaltrials.org and will include a complete statistical analysis plan submitted to publication.

8. Study plan

A general layout of the study is provided in Appendix 1. In the outpatient clinic, the screening procedure will be performed among patients planned for TKA by the surgeons. Patients will be asked by orthopedic staff whether they may be contacted regarding the research project. The research staff will then contact potential patients either in person or via telephone. The written study information will be explained – either at the outpatient clinic or via telephone by the investigator.

All patients receive both spoken and written information. Information is given in a separate closed room without interruptions. All patients are given the chance of an additional meeting with the chance of bringing a relative. All patients must give a signed informed consent on paper prior to inclusion to participate in the study. The patient will sign the consent form on day 1 after surgery.

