8.3 Study specific

Pain is rated by the patient before the intervention, after the initial LA injection, at home on days 2-7 and at the 2-, 4-, 12-, and 24 weeks follow-up via telephone.

A Visual Analog Scale (VAS 0-100) is used. On days 1-7 patients mark their pain in the electronic CRF twice a day (Appendix 5). If the patient is not able to complete the ratings electronically, a physical pain diary will be provided. Pain is rated by the patient at rest, during a 5-meter walk test, and during sleep. At the hospital and at the follow-ups patients are asked to rate their pain at rest and during a 5-meter walk test.

Use of rescue-analgesics (opioids) or other specific pain-relieving actions that differ from standard treatment is noted in the CRF.

The presence of dysesthesia or other side effects will be evaluated at each follow-up.

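### The primary outcome totals 6 or 12 home walk-pain ratings, but the plan gives no cumulation formula or rule for missed ratings and uses a test that needs one complete value per patient

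*Combined protocol and SAP*

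**What the plan says.** Section 3.1 defines the primary outcome as "Cumulated pain (VAS 0-100 mm) upon ambulation in a 5-meter walk test on days 2-7 postoperatively after TKA surgery". No formula follows. Section 7.1 gives a mean of 390 (SD 208) for this quantity in the team's previous study. On a 0-100 scale that must be a total or an area under the curve, not an average.

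Section 8.3 describes the collection: "On days 1-7 patients mark their pain in the electronic CRF twice a day". Ratings cover rest, the walk test and sleep, with a paper diary for patients who cannot enter them electronically. It does not say whether the walk test is rated at both daily entries. Section 10.1 makes the pain scores source data registered directly in REDCap.

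Section 7.2 compares the primary endpoint by independent-samples t-test or Mann-Whitney test, in both an intention-to-treat and a per-protocol population. On gaps it says "Missing values will be accounted for in the final statistical plan". It also promises a complete statistical analysis plan, which is not in the documents.

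Section 7.1 states "In a two-sided superiority design with a level of significance of 0.05 and a power of 80% we need two groups of 18 patients each", and then "Assuming a small number of dropouts, 22 patients will be included in each of the two groups".

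**The concern.** A t-test or Mann-Whitney test takes one number per patient. When that number is built from 6 or 12 self-entered home ratings, someone must decide what it is for a patient with a gap. Zero-filling, deletion, averaging and imputation are all still open, and they can give different primary results from the same data.

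Two of these choices would be damaging. Restricting the analysis to complete patients costs power, because a single gap among many ratings loses the whole patient. Summing only what was entered scores a gap as no pain, so the arm that skips more looks better. Skipping could plausibly be related to pain, sedation or re-admission, although the documents give no evidence on this.

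The sample size contains no explicit provision for missed single ratings.

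**Working it through.** **Inputs.** From section 7.1: control mean 390, SD 208, a 50% reduction, two-sided alpha 0.05, power 80%, 18 per group raised to 22. From sections 3.1 and 8.3: six days, so 6 ratings if the walk is rated once a day and 12 if twice. Missed-rating rates are not in the documents; those below are assumptions.

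**The plan's own figure.** The target difference is 0.5 × 390 = 195, and the standardised difference is 195/208 = 0.9375.

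n = 2 × [208 × (1.960 + 0.842)/195]² = 17.86, rounded up to 18 per group. This reproduces the plan. The t-based calculation gives 18.87, or 19. The allowance is 4/22 = 18.2% of patients. With all 22 per group complete, t-test power is 86%; with 18 it is 78%.

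**If only complete patients were analysed.** Let p be the chance that a rating is missed, independently across m ratings, with no whole-patient dropout. The expected number complete is 22 × (1 − p)^m. Setting this to 18:

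- m = 6: p = 1 − (18/22)^(1/6) = 3.29%
- m = 12: p = 1 − (18/22)^(1/12) = 1.66%

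| Ratings | Missed | Fraction complete | Complete per arm | Power |
|---|---|---|---|---|
| 6 | 3% | 0.833 | 18.3 | 79% |
| 6 | 5% | 0.735 | 16.2 | 73% |
| 6 | 10% | 0.531 | 11.7 | 58% |
| 12 | 3% | 0.694 | 15.3 | 71% |
| 12 | 5% | 0.540 | 11.9 | 59% |
| 12 | 10% | 0.282 | 6.2 | 32% |

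**If misses cluster within patients.** With a beta-binomial model and 10% missed, an assumed within-patient correlation of missingness of 0.3 gives power of 71% (6 ratings) or 65% (12). A correlation of 0.5 gives 76% or 73%. At 5% missed, the corresponding figures are 79% or 76% (correlation 0.3) and 81% or 80% (correlation 0.5).

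**If gaps were summed as zero.** With 10% missed in both arms, the totals of 390 and 195 become 351 and 175.5, so the difference shrinks from 195 to 175.5. In simulation (22 per group, assumed correlation of 0.6 between a patient's ratings) power stays near 84-86%. The harm comes from unequal skipping: 10% extra misses in one arm at a mean of 390, with no true effect, gives a false difference of 0.10 × 390 = 39, which is 39/195 = 20% of the target.

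**If the available ratings are averaged and scaled up.** In the same simulation, with 10% missed at random, power is about 85% (6 ratings) or 86% (12).

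**The case against.** A reader might infer that each missed rating must either count as zero or remove the patient, and that the trial can absorb only 1.7-3.3% missed ratings. The documents do not support that. Section 7.2 defers the rule, so prorating and imputation remain open. Its intention-to-treat population is every eligible randomised patient, which argues against deletion in that analysis. Only the per-protocol definition and the description of a completed patient in section 17.2 point towards removal. The 1.7-3.3% range is a property of complete-case analysis with independent misses and no dropout, not of the trial as designed.

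A reader might also infer that a total compared by t-test cannot be rescued by any missing-data rule. It can: a prorated total under the planned test would recover most of the power if misses were random, as the last simulation shows.

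Two further points stand. The larger losses depend on 12 ratings, which is not established. A mean of 390 is 65 mm per rating over 6 but 32.5 mm over 12, in patients selected for a walk VAS of at least 45; this suggests one rating a day without proving it. And the size of a zero-fill bias depends on the arm: the same 10% excess at a mean of 195 shifts that arm by 19.5, not 39. The paper diary should also prevent some gaps.

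What remains is that the formula, the number of ratings and the rule are undefined, and that the stated test makes no direct use of partial data or of the 24-hour walk VAS.

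**Conclusion.** The concern holds in a conditional form. The plan leaves the primary estimator open at the point where home-diary data are most likely to have gaps, and its allowance names only dropouts.

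The possible cost ranges from almost nothing, if available ratings are averaged and misses are random, to power of 59% (12 ratings) or 73% (6 ratings) at 5% missed under complete-case analysis with independent misses and no dropout. Clustering moves those figures back towards 80%; whole-patient dropout moves them down. Zero-filling threatens bias rather than power.

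All missed-rating rates are assumptions, so no particular loss is predicted. The change should be made because it closes an open choice in the primary analysis, uses partial data and costs little.

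**What to change.** Before unblinding, amend section 3.1 and the statistical plan as follows.

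- State how many walk ratings per day enter the primary outcome.
- Define the outcome as the mean walk VAS over days 2-7. Multiply by the scheduled number of ratings to report it on the cumulated scale.
- Replace the unadjusted test with a linear mixed model on all recorded walk ratings, with arm, day, arm-by-day and the 24-hour walk VAS. The primary result is the arm contrast averaged over days 2-7.
- State that a missing rating is never scored as zero.
- Add one sensitivity analysis that shifts missing ratings upward in the cryo arm by pre-stated amounts.

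The 24-hour walk VAS is already collected for eligibility, and section 7.1 reports it as the best predictor of the outcome. Adjustment should therefore gain precision, though the documents give no correlation from which to size the gain.

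The cost is revised wording and slightly more analysis, with no new patients, visits or data. The model relies on ratings being missing at random, which the sensitivity analysis probes. A prorated total with a minimum number of ratings, or multiple imputation, would also close the gap in the rule; the mixed model is preferred because it handles partial data and the baseline adjustment in one step.

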8.1 Perioperative treatment

The pre-, intra-, and postoperative treatment-course follows the local operating procedures and common clinical guidelines implemented at the Dept. of Orthopedic Surgery, Hvidovre Hospital.

8.1.1 Preoperative standard treatment

Preoperatively, the patient is examined by a specialized arthroplasty surgeon, and a basic preoperative health examination is done, along with a specialized anesthesiologic assessment planning the anesthesia for the TKA operation.

On the morning of surgery the patient will be given:

Celebra	400 mg
Paracetamol	1 g

8.1.2 Anesthesia

All included patients will receive general anesthesia or a neuraxial blockade in the form of a spinal anesthesia administered at level L2-L4, by injecting 2-3 ml of hyperbaric bupivacaine 0.5%. If spinal anesthesia is performed, perioperative sedation with propofol or other sedatives is optional and done in agreement with the patient. According to local guidelines, dexamethasone 0.3 mg/kg or 1 mg/kg IV rounded up to nearest 10 mg will be administered prior to surgery to patients with a pain catastrophizing scale score ≤ 20 or > 20 , respectively [27]. A supplement of local infiltration analgesia is administered directly into the surrounding tissue of the knee at the end of surgery, according to local operating procedure.

Tranexamic acid is administered as 1 g preoperatively, 1 g 3 h postoperatively, and 1 g in the surgical ward according to local operating procedure to prevent bleeding.

8.1.3 Surgical procedure

A medial parapatellar approach will be used. No tourniquet is used. Following insertion of the prosthesis, local infiltration analgesia (LIA) with 200 mL 0.2% Ropivacaine will be injected in the posterior capsule, periarticular tissues and subcutaneous tissue. Joint capsule, subcutis and skin are closed with standard 3-layer closure and a compression bandage is applied. No drains are used. All patient will be operated with cemented components and patella resurfacing.

8.1.4 Standard postoperative treatment

The postoperative multimodal analgesic regimen consists of:

Celebra 200 mg x 2, for 7 days.
Paracetamol 1 g x 4, for 7 days.
Morphine 10-20 mg or opioid equivalents administered only as rescue opioids.

8.2 Intervention

The intervention will take place after the inclusion at 20-32 h after TKA surgery. The procedure will be performed at the Dept. of Anesthesiology.

8.2.1 Cryoneurolysis mechanism of action

Cryoneurolysis will be performed on the superficial genicular nerves (Cryo-S, Metrum Cryoflex, Blizne Laszczynskiego, Poland). The cryoprobe works by passing carbon dioxide at a relatively high pressure down the shaft, through a small orifice and into a closed tip at a much lower pressure. According to the Joule-Thomson effect, this drop in pressure causes a dramatic decrease in temperature which leads to a rapid expansion and absorption of heat. Afterwards the gas moves back up through a larger diameter tube. Importantly, this closed loop allows no gas to escape into the surrounding tissue. The intense cold created (approximately -70°C) causes a Wallerian degeneration, thereby reversibly destroying the nerve axon with retention of the endo-, peri-, and epineurium. Since the architecture of the nerve remains intact, the nerve axon can grow out along its normal path which occurs with approximately 1-2 mm/day [28]. The drop in temperature cannot be lower than the boiling point for the gas used, which for carbon dioxide is -79°C. Irreversible degeneration of nerve tissue occurs at about -100°C which allows for a wide safety margin.

8.2.2 Procedure technique

Cryo-group:

The patient is placed in a supine position with a sheet between the upper and lower part of the body, thus blinding the patient from the intervention allocation. The procedure is performed using a linear array ultrasound probe. Local anesthesia is injected in the skin. The superficial genicular nerves, more specifically the ISN and the AFCN, are visualized. A nerve stimulator (Stimuplex HNS 12, B Braun, Melsungen, Germany) is used to verify the visualized nerves., 2-3 ml of ropivacaine 5 mg/ml is injected around the nerves. After 5-15 minutes the effect is evaluated by assessing pain in the surgical area and asking the patient whether there is a pain relief. Following this evaluation, cryoneurolysis (Cryo-S, Metrum Cryoflex, Blizne Laszczynskiego, Poland) is performed unilaterally along a treatment line, the location of which was guided by visualization and palpation of anatomic landmarks. The ISN treatment line is located along the line that connects a point located 5 cm medial to the lower pole of the patella and a point located 5 cm medial to the tibial tubercle. The AFCN treatment line is located at one-third the length of the distance from the center of the patella to the top of the femur, with a width equal to the width of the patella.

Sham-group:

The exact same procedure as in the cryo-group is performed, except that the nerves are not frozen with the cryoneurolysis apparatus. Sound effects from the machine are replicated to give the patient the same experience as in the active intervention group.

8.3 Study specific

Pain is rated by the patient before the intervention, after the initial LA injection, at home on days 2-7 and at the 2-, 4-, 12-, and 24 weeks follow-up via telephone.

A Visual Analog Scale (VAS 0-100) is used. On days 1-7 patients mark their pain in the electronic CRF twice a day (Appendix 5). If the patient is not able to complete the ratings electronically, a physical pain diary will be provided. Pain is rated by the patient at rest, during a 5-meter walk test, and during sleep. At the hospital and at the follow-ups patients are asked to rate their pain at rest and during a 5-meter walk test.

Use of rescue-analgesics (opioids) or other specific pain-relieving actions that differ from standard treatment is noted in the CRF.

The presence of dysesthesia or other side effects will be evaluated at each follow-up.

8.4 Other clinical data

- Demographical data (gender, age, height, weight, co-morbidity, American Society of Anesthesiologist (ASA) score)
- Preoperative opioids/strong analgesics
- Pain Catastrophizing Scale (PCS)
- Surgical data (date of surgery, indication, surgical time, procedure information, intraoperative bleeding, transfusion data, perioperative analgesics)
- Type and dosage of analgesics.
- Deviations from standard treatment
- Quality of sleep, lethargy, dizziness, and nausea, pre- and postoperative registration, on a NRS (0-10)
- Adverse events throughout the hospitalization and at each follow-up
- Neuropathic Pain Scale for Postsurgical Patients (NeuPPS)

8.4.1 Pain Catastrophizing Scale

The PCS consists of 13 questions divided into three sections: rumination, exaggeration, and helplessness [27, 29, 30]. The questions are answered in accordance with a scale of 0 to 4. At Hvidovre Hospital all patients undergoing major lower limb arthroplasty fill out this form prior to surgery.

8.4.1 Neuropathic Pain Scale for Postsurgical Patients

The NeuPPS consists of 5 yes/no questions about the presence of sensory disturbances [31, 32]. A score of 1 will be assigned for a 'yes' and a score of 0 will be assigned for a 'no'. The summed scores are used. The patients will fill out this questionnaire preoperatively and at every follow-up.

8.5 Study location

The inclusion will take place at the Dept. of Orthopedic Surgery, Arthroplasty unit at Hvidovre Hospital, Capital Region of Denmark. Study personnel include employees from the Dept. of Orthopedic Surgery, the Surgical Wards and the Dept. of Anesthesiology, at Hvidovre Hospital.

The sponsor and investigators are employees at the Research Unit at the Dept. of Anesthesiology, Hvidovre Hospital.

8.6 Timespan

The study is expected to start inclusion during the fall of 2023.
The expected end of inclusion is in the spring of 2024.

9. Study drugs

9.1 Ropivacaine

The cryoneurolysis intervention itself does not involve any study drugs. However, ropivacaine 5 mg/ml will be administered preceding the cryoneurolysis or the sham block. The ropivacaine is contained in plastic ampules.

9.2 Rescue drugs

It is not expected that any specific rescue drugs are needed. However, drugs that the investigator may find necessary to use include adrenaline, atropine, intralipid, midazolam, or ondansetron. The administration of rescue drugs will be recorded in the patient's CRF

10. Data recording, management, and quality

The study is to be conducted in accordance with the current guidelines for quality management and control for clinical investigations with human subjects. The study will follow Good Clinical Practice (GCP) guidelines at all times.

The sponsor is associated with Hvidovre Hospital, and is responsible for handling and storage of data, in accordance with current updated guidelines including the Danish Data Protection Act, the General Data Protection Regulation and the Health Act.

Data belongs to the sponsor and will be kept 5 years after the end of the trial.

The study is submitted to the Data Protection Agency for approval.

Signed informed consent from participating patients at Hvidovre Hospital will be stored in a locked cabinet at the Anesthesiologic Dept. 542, in the office 500.50.401, cabinet F. All other data will be stored in REDCap.

10.1 Case report form

Every patient included in the study will have an electronic CRF in the data-monitoring system REDCap. The following will be considered as source data and registered directly in REDCap: Pain scoring at all time points, evaluation of sleep quality, lethargy, dizziness, and nausea in the 7 days following surgery, use of rescue analgesics after discharge, and presence of side effects at follow-ups.

10.2 Blood samples

No study-specific blood samples will be taken.

10.3 Education

The primary investigator will ensure that the personnel, and patients participating in the study, have received correct and sufficient education regarding the study. Procedural descriptions will be made for different types of personnel, accounting for different types of tasks.

An overview of the entire study and study plan will be accessible for the participating personnel on site.

11. Ethical considerations

11.1 General ethics

The study will be carried out in accordance with the principles in the Helsinki Declaration, and the protocol will be submitted the Local Ethics Committee (LEC), the Danish Medical Agency (DKMA) and the Data Protection Authorities (DPA) for approval. The investigators are required to inform the relevant authorities (LEC, DKMA, DPA) on substantial or essential changes in the protocol.

All patients participating in the study must provide a signed informed consent form before inclusion in the study. The patients will be informed that the consent includes access to information in relevant EPJ in relation to their surgery and during the follow-up time until End-of-Trial. This information will also be provided to the authorities in case of inspection. This is in accordance with the Health Act (Sundhedsloven), § 43, stk. 1.

It is the responsibility of the investigators to ensure that all patients receive written information about the study in connection with their hospitalization, and to ensure that all patients are informed about the study. This is to ensure that the patient is fully aware of all aspects of participating in the study. The patient can at any time withdraw their consent to participating in the study, and this will not have any consequences on the treatment the patient receives or deteriorate the relationship between the patient and the treating personnel. The patient will continue to receive the best treatment the facility can offer.

